4.2 Data Entry Methods

The data for this study will be recorded in a REDCap database (REDCap Consortium, Vanderbilt University) in the secure regulated environment (rStats) at the University of Massachusetts Medical School. This Unix-based environment is not accessible from outside of the medical school and only medical school staff with IRB approval are assigned an account in this environment. We will program the system for a single entry with validation rules for validity, consistency, and normal range values at the time of entry and comprehensive edits through multivariable edit approaches conducted after the data have been submitted to the main data base. Edit queries will be resolved by clinic staff with corrections posted to the database through the REDCap system, which enforces an audit trail for all changes.

The main study database will be stored on a secure server in the University of Massachusetts HIPAA-compliant data center with daily back-up. REDCap will be used within the rStats environment to protect any PHI/PII data that are collected as part of the study. We will strive to minimize collection of such data and REDCap will be programmed to segregate that data from the main study data so that exports for analysis will be deidentified.

Data will be exported from REDCap for import into the latest version of statistical software (e.g., SAS, SAS Institute, Cary, NC) for all analysis. All reports and analyses will be generated from these files using the latest version of SAS (currently SAS 9.3). Data files (and accompanying SAS programs) that are used for reports, presentations, or publication will be archived as required past the end of the study. The REDCap system will be programmed and maintained by study staff at the U Mass Medical School while data entry will be performed by research study staff at the U Mass Medical School and at the U Pittsburgh Medical School.

To the extent possible, data from the laboratory assays will be conveyed electronically and uploaded directly into REDCap. Edit checks will be built into the upload process to identify any out-of-normal range values. Any edit queries will be forwarded to the appropriate laboratory for resolution. If a direct upload is not possible, a REDCap data entry screen will be implemented for the laboratory data.

4.3. Data Analysis Plan

4.3.1. Overview. Table 1 provides a summary list of outcome variables for each Specific Aim. Descriptive statistics will be calculated (means/SD or median/IQR) by treatment group. Because infants will be repeatedly observed and measured, initial analyses comparing outcomes between the treatment groups (SVS vs SCC) will be conducted using standard approaches assuming a normal distribution (i.e., two-sample t-test) or using non-parametric alternatives if assumption of a normal distribution is not appropriate (i.e., Mann-Whitney U Test). We will use mixed effect models to analyze the repeated measures over time. These models will estimate the trajectory of outcomes over time within each treatment group as affected by condition and other factors of interest. The time metric for these models will be hrs since birth for Aims 1 and 2 for each measurement so that the trajectories will relate to the same baseline

measurement for all infants. Treatment group will be considered as fixed effect in the models, with other factors considered to be either fixed or random effects, depending on the nature of the factor: opioid only vs opioid+other; gender, delivery mode (vaginal or caesarean-section); delivery anesthetics (none vs anesthetics). Comprehensive histories from medical record and questionnaire will allow us to examine the influence of additional variables

4.3.2 Specific Aim 1: We will use mixed effects models as described above to examine whether infants treated with SVS compared to SCC have: 1) Lower daily average and maximum NAS scores; 2) Less morphine requirement (primary pharmacological treatment for managing NAS at both sites; cumulative dose normalized for body weight); 3) Enhanced velocity of weight gain throughout hospitalization; and 4) Shorter hospitalization length of stay. A model will be fit for each outcome using Nagelkerke's R² to determine the model with the best fit using the ratio of the -2 log likelihoods for the model with covariates compared to the intercept-only model. Factors of interest will be included in the model as appropriate and interactions with treatment group will be tested as well. The interactions will indicate whether the treatment effect is the same across subgroups. Additional analyses to identify groups of infants who do particularly well (or poorly) with SVS will be conducted using latent class techniques, such as cluster analysis (for continuous variables) or latent class analysis (for discrete variables). The factors of interest will include: drug exposure (e.g., prescribed maintenance therapy, prescription drugs and illicit substance; with or without poly-drug use), demographic data (gender, race, gestational age, birth weight, birth head circumference, delivery mode, anesthesia at delivery), and feed type (formula or breast milk).

Movement: Actigraphy (movement activity frequency) will be compared across days and between Groups using similar mixed effects models as above. The outcomes of interest are actigraphy throughout hospitalization to determine if SVS reduces movement and increases quiescence episodes over time (12 and 24 hour assessments) compared to SCC.

4.3.3. Specific Aim 2: Study design allows systematic quantification of condition effects on breathing (IBI variance and respiratory rate), cardiac rhythm (R-R variance and heart rate), movement activity (frequency and duration), blood oxygenation (durations<85%), and skin temperature. Histogram of frequency-bands of cardio, respiratory and movement incidents will be determined. As with Aim 1, mixed effects models will be used to examine if SVS, within infants and between SVS and SCC infants: 1) Decreases irritability and sleep disruption/fragmentation indexed by movement frequency and duration; 2) Improves cardio-respiratory control: reduces bradycardia/bradypnea. tachycardia/tachypnea and increases incidents of eucardia/eupnea; and 3) Reduces other NAS symptoms: e.g., temperature; oxygenation. Additional computational signal analysis. We have developed novel statistical point process algorithms that measure cardio-respiratory dynamics and movement over continuous time domains.^[67, 68]The variable characteristics of respiratory (IBI) and cardiac (RR) signals are integrated with the dynamic characteristics of these signals to provide instantaneous, moving estimate of mean, variance and other dynamic measures (e.g., spectrum, poles, frequency).^[68] These measures will be used to examine temporal dynamics of respiratory and heart rate rhythm, and explore corresponding physiological relationships with movement over time; e.g., Do IBI changes that reflect caudal brainstem function precede cortical behaviors such as arousal (e.g., movement)? Time series of movement periods will be analyzed using Wavelet derived SAP throughout stimulation ON and OFF to evaluate temporal dynamics including: 1) Response time for improvement in rhythm relative to the onset of stimulation; 2) Whether there is loss of efficacy over time (during each 30 min stimulus period as well as from one period to the next); 3) Whether improvement in rhythm persists following offset of stimulation.

4.3.4. Specific Aim 3. One-Year Outcomes' Assessment. We will use a general linear model approach to analyze outcomes over one year, using the same model building strategies described above. Some outcomes, such as the Bayley-III scales, are collected at multiple follow-up visits so we will use mixed effects models to estimate treatment effect over time and to adjust for other covariates. Impairment is determined based on a fairly extensive neurobehavioral test battery but the component test scores are highly correlated. To control for error that results from this correlation, we will reduce the number of tests by evaluating the domain or summary scores from the various instruments and use the approach of Ingraham and Aiken^[69] to determine how many deviant scores are required to identify a child as impaired. This approach calculates the criteria for abnormality when employing batteries of multiple tests by generating probability curves for exceeding cut-off criteria by chance given certain criteria (e.g., an expectation that one group will show a decrement). This type of analysis will allow us to look at rate of impairment in young children with opioid exposure and assess whether SVS compared to SSC reduces likelihood of impairment.

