2.1.1. Investigational Device. Stochastic Vibrotactile Stimulation (SVS). The

infant's crib mattress will be replaced with a specially constructed mattress (noncommercially available) to provide gentle vibrations and sounds during mattress stimulations. The mattress is embedded with mechanical actuators that provide wholebody SVS (30-60Hz; ~10-12µm RMS). Co Fab Design, LLC will construct the mattresses and drivers as per the design documents furnished under Confidentiality Disclosure Agreement (CDA; University of Massachusetts Medical School/Wyss Institute-Harvard University patent: PCT/US2015/021999) for research purposes only as per the licensed mattress assembly and electrical assembly and verification documentation; device components may be modified with improved technologies that provide equivalent mattress output to help ensure consistency of mattress integrity over time. Engineers from the Wyss Institute and the University of Pittsburgh will provide assistance in the build to ensure it performs as per the original patent documentation.

2.1.2. Study Design/Type. This study is a randomized, placebo-controlled, parallel group clinical trial. Eligible patients will be randomized into one of two groups in a 1:1 ratio, matched for gender, to either (1) SVS or (2) SCC:

1) SVS. Experimental Intervention: Newborn infants at-risk for NAS due to opioid exposure *in utero* randomized to this arm will receive daily intervals of continuous SVS (ON) and no SVS (OFF) throughout hospitalization, starting within 30-hrs post birth. An automated control box will be set to deliver continuous alternating 3-hr cycles of ON/OFF intervals. A stimulation period will always be followed by an interval of no stimulation; in any 24-hr period an infant will not receive more than a total of 12 hrs of stimulation (should the infant remain in the crib throughout an entire 24 hr period). Notably, infants are not always in their crib and it is not feasible to provide round-the-clock research staffing to monitor when the infant is in or out of the crib (e.g., being held

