2.4 Sample Size and Power Calculations

For all Aims there is sufficient sample size to detect clinically meaningful differences with 90% power, described below:

2.4.1. Specific Aim 1. We use the Finnegan NAS score as the primary outcome for this aim. From Nayeri et al. [70] and our own pilot data, the Finnegan NAS score in opioid-exposed infants had a SD of 2.0-2.5. Assuming a standard t-test with a two-sided alpha level of 0.05 for the unadjusted comparison of the Finnegan scores at a particular time point with the more conservative standard deviation (SD.=2.5), the sample size of 115/group can detect a difference of 1.1 with 90% power. Taking into account the repeated measures of the Finnegan NAS score, assuming intra-infant correlations of 0.5-0.7, we will have 90% power to detect a difference of 0.80-0.95 in a mixed effects model for the overall (i.e., across time) treatment group coefficient. With a mixed effects model, we will also add covariates as described above to determine an adjusted treatment effect. We expect that this model may have even more power than described here due to the partitioning of the overall variance among the covariates. Because infants are hospitalized and under observation until release, we expect only minimal attrition and loss of information.

2.4.2. Specific Aim 2. We use Movement as primary outcome for this aim. Based on our preliminary data in 26 NAS infants (OFF: mean movement 40% of condition time, SD=10%; ON: mean movement 26% of condition time, SD=9%) and

assuming a two-sided paired t-test at alpha=0.05 for the unadjusted treatment effect, we estimate 25 infants per group will give us 90% power to detect a reduction of 7% in movement between the two treatment groups (a relative reduction of about 20% from 40% in OFF to 33% in ON) with a conservative SD of 10% (from the pilot study).

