2) Chart Review/Bedside Log. NAS severity scores. The infant's clinical-care nurses at each site are routinely trained on the NAS assessment tool (modified

Finnegan Scale)^[63] as part of clinical education; this helps ensure reliability of scores. Nurses score the infants' withdrawal severity ~every 3-4 hrs to assess changes in central, autonomic, vasomotor and gastrointestinal function. Daily NAS scores, weight (gain/loss; trajectory), head circumference, routine feed type (formula or breast milk), pharmacological management (medication, dose normalized for body weight), and birth date and date of hospital will be obtained from medical and/or nursing chart review. A computerized and/or paper log (de-identified, subject id only) will be kept by the infant's bedside to record when the infant is in the crib, and nursing/parent interventions (e.g., feeds, diapering, caregiver cuddling, and placement in motorized swings). This provides some indication of the infant's routine clinical care since investigators cannot be at the bedside 24/7. A separate log kept by investigators will be used to record preprogrammed time onset and offset of SVS (i.e., to verify daily automated SVS coinciding with log indicating when infant is in the crib to receive the intervention). Data will be entered by a research investigator via secure password protected computer into REDCap database.

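### The Aim 1 NAS model counts time from birth and leaves baseline and the start of the outcome series undefined, so pre-randomisation scores may dilute the powered effect and go unused as a covariate

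*Combined protocol and SAP*

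**What the plan says.** Section 4.3.1 fixes the axis: "The time metric for these models will be hrs since birth for Aims 1 and 2 for each measurement". The reason it gives is "so that the trajectories will relate to the same baseline" measurement, but no section defines that measurement.

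Section 2.1.2 has SVS given "throughout hospitalization, starting within 30-hrs post birth", and the SCC arm is enrolled in the same 30-hour window. The Background (section 1) gives 24 hours; the two passages need to be reconciled.

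Under section 4.1.1, nurses score "withdrawal severity ~every 3-4 hrs to assess changes in central, autonomic, vasomotor and gastrointestinal function", and daily scores are abstracted from the chart. The NAS outcomes in section 4.3.2 are each day's mean and highest score. No rule says which score or day opens the series.

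The factors named in sections 4.3.1 and 4.3.2 cover drug exposure, demographic, birth and delivery characteristics, and feeding. Neither list contains an early NAS score. Section 4.3.1 leaves room for further unnamed variables, and section 4.3.2 judges candidate models by fit.

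The quantity powered for repeated scores in section 2.4.1 is the overall treatment coefficient across time.

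**The concern.** An axis that starts at birth aligns infants by age. It does not give them a shared measurement taken before treatment, because the time from birth to treatment start can differ from infant to infant by up to 30 hours.

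Two things follow. First, scores charted before randomisation cannot differ between arms except by chance. If they sit in the outcome series, they average zeros into the across-time coefficient. A first-day mean can mix scores from before and after randomisation, and a first-day maximum can come wholly from before it. Second, the same scores are an early measurement of the outcome itself, already being abstracted, and could remove between-infant variance if used for adjustment.

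The plan's silence matters in its own right. Keeping, dropping or adjusting for these scores could be settled after the data are seen.

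**Working it through.** **Inputs from section 2.4.1.** "standard t-test with a two-sided alpha level of 0.05"; SD 2.5; 115 per group; 90% power; intra-infant correlation ρ of 0.5-0.7.

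**Inputs from elsewhere in the plan.** Treatment start up to 30 h after birth (2.1.2); scoring every 3-4 h (4.1.1).

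**Assumptions not in the documents.** Stay of 5-20 days; treatment start at 12-30 h; correlation r between the baseline score and a later score of 0.2-0.3, with 0.5 shown for comparison; equal correlation between all days.

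**1. The plan's own figures.**
- The plan states that "the sample size of 115/group can detect a difference of 1.1 with 90% power". Detectable difference = (1.960 + 1.282) × 2.5 × √(2/115) = 1.07, which rounds to 1.1. Power at exactly 1.1 is 91.6%. The figure reproduces.
- For repeated scores the plan says: "assuming intra-infant correlations of 0.5-0.7, we will have 90% power to detect a difference of 0.80-0.95". The formula is 1.069 × √[(1 + (m − 1)ρ)/m] for m scores. The plan does not state m. With m = 3 the range is 0.87-0.96, with m = 8 it is 0.80-0.92, and with m = 10 it is 0.79-0.91. No single m gives both stated ends, but the scale agrees.

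**2. How many scores are at issue.** 30 h at one score per 3-4 h is 30/4 to 30/3, or about 7-10 scores. As daily summaries this is 30/24 = 1.25 days.

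**3. Dilution if pre-treatment scores are kept as outcomes.** The share of the series before treatment is f = start time / (24 × days of stay), and the expected across-time coefficient is (1 − f) times the post-start effect. With the true effect set to give 90% power when every day is a treated day, power = Φ[3.242(1 − f) − 1.960].

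| Stay | Start | f | Power |
|---|---|---|---|
| 20 days | 12 h | 12/480 = 2.5% | 88.5% |
| 10 days | 24 h | 24/240 = 10% | 83.1% |
| 10 days | 30 h | 30/240 = 12.5% | 81.0% |
| 5 days | 30 h | 30/120 = 25% | 68.1% |

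At 12.5%, a post-start effect of 0.80 would appear as 0.80 × 0.875 = 0.70. The arithmetic is for daily averages; daily maxima do not average in this way.

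**4. Leaving those scores out of the outcome.** For a 10-day stay with one pre-treatment day, power returns to 89.7-89.9%.

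**5. Using them as a covariate.** With 10 post-randomisation daily scores, detectable difference = 1.069 × √(v − r²), where v = ρ + (1 − ρ)/10.

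| ρ | v | No covariate | r = 0.2 | r = 0.3 | r = 0.5 |
|---|---|---|---|---|---|
| 0.5 | 0.55 | 0.79 | 0.76 | 0.72 | 0.59 |
| 0.7 | 0.73 | 0.91 | 0.89 | 0.85 | 0.74 |

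The reduction is about 3-9% at r of 0.2-0.3 and 19-26% at r of 0.5. In the setting of step 4, power rises to 91.4-91.7% at r = 0.2 and to 93.2-94.1% at r = 0.3.

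**6. The alternative model.** A generalised least squares check at ρ = 0.5 and 10 days, with early scores kept in the response but arm means constrained to be equal before treatment, gave a standard error of 0.182. The baseline-covariate analysis gave the same value.

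**The case against.** A reader might infer that the plan analyses pre-treatment scores as outcomes. It does not say so. Section 2.1.4 has participation begin within 30 hours of birth, which fits a series opening at enrolment equally well. What can be shown is that the start of the series and the baseline are undefined.

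Hours since birth is also a defensible axis for a condition that evolves with age, and section 4.3.1 estimates a trajectory within each arm. In such a model the treatment effect can show as later divergence. Keeping early scores in the response does not by itself waste precision, as step 6 shows. The plan, however, states no constraint of equal starting means, and the quantity it powers is the across-time coefficient.

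It is tempting to treat 12.5% as an upper bound. It is not: it assumes a 10-day stay and a 30-hour start for every infant, and the documents give neither a length of stay nor a distribution of start times. Shorter stays give more dilution; longer stays or earlier starts give less.

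The large precision gains need an early-to-late correlation of 0.5 or more. The plan's 0.5-0.7 is a general within-infant figure, and first-day scores, taken while withdrawal is still emerging, may correlate less with later ones. At 0.2-0.3 the gain is modest.

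All of these limits stand. None of them supplies the missing definitions.

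**Conclusion.** The point holds as a gap in specification with a conditional cost. The birth-based axis gives no common pre-treatment baseline, no rule removes pre-randomisation scores from the NAS outcome series, and no pre-treatment score is a named covariate.

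If the early scores are kept as outcomes and the across-time coefficient is tested, the effect is diluted by about 2.5-25% and power falls from 90% to about 68-88.5% over the assumed stays and start times. The bias is toward no effect. It does not reach single-time-point comparisons after treatment has begun, length of stay or treatment-by-time contrasts. It concerns NAS scores; actigraphy starts only at 24-48 hours.

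The covariate lowers the detectable difference by about 3-9% at the assumed correlations, and by more if the correlation is higher. This is an inexpensive improvement worth making. It does not show that the planned analysis is invalid.

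**What to change.** State in section 4.3 that:

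- Only scores charted after randomisation are outcomes. The first-day average and maximum are computed from those scores alone.
- Baseline is the mean of the Finnegan scores charted before randomisation. It enters as a pre-specified covariate that is not subject to selection by model fit. Where an infant has none, fill in a constant and add an indicator for the missing value.
- Alternatively, pre-randomisation scores stay in a longitudinal model constrained to equal means in both arms before randomisation.
- Hours since birth remains in the model as an age term.

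The cost is SAP wording, plus the time of randomisation and of each score in the analysis file; the scores already come from chart review. There are two limits. Some infants enrolled early will have no pre-randomisation score and gain nothing from the covariate. Scores between randomisation and the start of SVS remain as outcomes, as an analysis by randomised group requires, so any dilution from that interval, whose length the documents do not give, is not removed.

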2.1.4. Study Duration. Subjects will participate in the study throughout their hospitalization, beginning within 30 hours post birth, and will be followed for up to 14 months post post-hospital discharge via medical records, telephone interviews, and return visits for outcome assessments.

2.1.5. Randomization. Random allocation of subject to treatment (SVS or SCC) will involve a permuted block design with random block sizes to assure equal treatment assignment for both treatments. We will stratify the randomization process by clinical site to force a balance between treatment groups and gender within each site. The random treatment assignments will be generated in SAS and uploaded into the IVRS system. The randomization process will verify patient eligibility before issuing treatment assignment. Treatment assignments will be in the form of mattress assignment tracked by the IVRS system based on admission and discharge information entered into REDCap (**See 4.2 below**). The IVRS system can be accessed by certified study staff

either through a telephone call or over the internet to a secure web site. The treatment assignments are recorded automatically in the REDCap system through an interface between the two systems and cannot be modified once imported from the IVRS system. The randomizations are monitored and verified by study staff on a routine basis. The IVRS also will monitor mattress availability and will notify study staff if a mattress of each type is not available for a randomization. (Maternal exposure will be stratified in the analysis).

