2.3 Inclusion/Exclusion Criteria

A total of 230 full-term (>37wks gestational age) newborn infants exposed to opioids *in utero* will be studied over the five-year funding period: 100 at UMass and 130 at UPitt.

2.3.1. Inclusion Criteria. Infant inclusion criteria include documented opioid drug exposure (i.e., positive toxicology screen; exposure questionnaire and medical record history) and comprise the general population (Worcester, MA and Pittsburgh, PA demographics) without restriction in regard to gender, race or socioeconomic status. Infants may also have additional prenatal poly-drug exposure (e.g., benzodiazepines, barbiturates, amphetamines, cannabinoids, alcohol, nicotine and/or caffeine). Inclusion of pregnant women is for the sole purpose of obtaining consent to study the infant post-delivery, and to review infant and maternal medical records. Pregnant women are included because we will be recruiting pregnant women who are at risk for delivering infants with NAS due to drug exposure in utero. Prenatal consents are needed to help expedite feasibility of study of infants soon after delivery. Infants will not be studied in utero, but will only be studied after delivery.

2.3.2. Exclusion Criteria. Subjects with clinically significant fetal anomaly, congenital abnormality, adverse pregnancy outcome, hydrocephalus or intraventricular hemorrhage >grade 2, seizure disorder not related to drug withdrawal, clinically significant cardiac shunt, anemia (hemoglobin<8g/dL), requires mechanical respiratory support or is being treated for MRSA or infection at the time of the study will be excluded, or other medical condition aside from NAS will be excluded. Informed consent will be obtained from parent(s) or legal guardian of all participants.

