2.4.3. Specific Aim 3. We use Bayley-III as primary outcome for this aim. We anticipate an attrition rate of ~40% in the 1-year follow-up assessments. Assuming a sample size of 60 children/group at 1 year with a two-sided standard t-test at alpha=0.05 and a SD of 14 for the Bayley-III cognitive composite scale, [71] we will have 90% power to detect a difference of 8.5 (or about a 12% difference) between the two groups at 1 year of age. The other Bayley scales have similar SDs, so the results will be similar. For a longitudinal analysis of the Bayley-III cognitive composite scale over the follow-up visits (1, 3, and 12 months of age), we will use a mixed effects model as above with months of age as the time metric in the model. Assuming the same sample size with intra-child correlations of 0.5-0.7 for a mixed effects model with a two-sided test for the treatment group coefficient at alpha=0.05, we will have 90% power to detect a treatment effect of 6.8-7.4 (depending on the correlation) using the treatment group coefficient. We can also add covariates to this model to estimate an adjusted treatment effect.

Each child will be classified as impaired or not based on the results of the battery of tests given over one year.[69] Assuming a worse-case scenario (in terms of SD of a proportion) of 50% impairment in the SCC group, with 60 children/group we will have 90% power to detect an unadjusted absolute improvement of 28% (50% vs. 78%) or a relative improvement of 56% in the SVS group with a z-test with a two-sided alpha =0.05. For an adjusted estimate of the improvement in percent impairment at one year, we will use a logistic model with other covariates added. For a longitudinal assessment of impairment, we will use a GEE longitudinal logistic model with the same approach for model building as above.

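### Randomisation is stratified by site with gender balanced within site, but the Aim 1 and Aim 3 analyses commit to neither factor; if site is prognostic the tests are conservative and some power is forgone

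*Combined protocol and SAP*

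**What the plan says.** **Design.** Section 2.1.2 says infants are "randomized into one of two groups in a 1:1 ratio, matched for gender". Section 2.1.5 specifies permuted blocks of random size and adds "We will stratify the randomization process by clinical site to force a balance between treatment groups and gender within each site". Site is therefore clearly a stratum. Gender is meant to be balanced within site, although the mechanism is not described. Section 2.3 sets the site sizes at "100 at UMass and 130 at UPitt".

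**Analysis.** Section 4.3.1 starts with a two-sample t-test, or a Mann-Whitney test if normality fails, and then moves to mixed models with treatment as a fixed effect. The other factors it names are "opioid only vs opioid+other; gender, delivery mode (vaginal or caesarean-section); delivery anesthetics (none vs anesthetics". Section 4.3.2 (Aim 1) adds drug exposure detail, race, gestational age, birth weight, head circumference and feed type. These enter at the analyst's discretion, and the model is chosen on Nagelkerke's R². Section 4.3.4 (Aim 3) reuses that model building. No analysis section names site as a covariate, stratum or random effect. The one commitment to stratify the analysis, in Section 2.1.5, concerns a different factor: "Maternal exposure will be stratified in the analysis".

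**Power.** Section 2.4.1 reports that "the Finnegan NAS score in opioid-exposed infants had a SD of 2.0-2.5" and takes 2.5. With 115 per group it claims 90% power for a difference of 1.1 at one time point. For repeated measures it says "assuming intra-infant correlations of 0.5-0.7, we will have 90% power to detect a difference of 0.80-0.95 in a mixed effects model". Section 2.4.3 (Aim 3) works from "Assuming a sample size of 60 children/group at 1 year", with SD 14 and a difference of 8.5.

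**The concern.** Stratified allocation removes between-site variation from the treatment contrast. An analysis without site puts that variation back into the error term, so the estimated standard error exceeds the true one. The test then rejects too rarely under the null and gives up power under the alternative. The same holds for gender so far as it is balanced by design.

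A site effect is plausible but not shown. Sections 2.1.2 and 4.1.1 leave drug treatment to each institution's medical team and NAS scoring to each site's nurses. Against that, both sites use the modified Finnegan scale and both use morphine as primary drug.

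At stake is efficiency and a discretionary modelling choice, not validity. Whether the stated 90% is also at risk depends on whether the quoted SDs are total or within-site, which the documents do not say.

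**Working it through.** **Inputs from the documents:** site sizes 100 and 130 (2.3); 115 per group, SD 2.5, difference 1.1, two-sided alpha 0.05 (2.4.1); mixed-model detectable differences 0.80 to 0.95 (2.4.1); 60 per group, SD 14, difference 8.5 (2.4.3). **Assumed:** the site gap D, from 0 to 1.0 within-site SD, with no other covariates in the model.

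**1. The plan's own figures.** Aim 1: the standard error is 2.5 × √(2/115) = 0.330, so 1.1/0.330 = 3.336 and power is Φ(3.336 − 1.96) = 91.6%. The exact 90% detectable difference is 3.2415 × 0.330 = 1.07, which the plan gives as 1.1. Aim 3: 8.5/(14 × √(2/60)) = 3.325, power 91.4%. Both stated figures reproduce.

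**2. Effect of omitting site.** With pq = (100/230)(130/230) = 0.2457, the estimated standard error is too large by the factor k = √(1 + 0.2457 D²).

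- True alpha = 2Φ(−1.96k).
- SD 2.5 read as *total*, effect set at the nominal 90%: power is Φ((3.2415 − 1.96)k) without site and Φ(3.2415k − 1.96) with it.
- SD 2.5 read as *within-site*, difference 1.1: power is Φ(3.336 − 1.96k) without site and 91.6% with it.

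| D (within-site SD) | k | True alpha without site | Total-SD reading: without / with site | Within-site reading: without / with site |
|---|---|---|---|---|
| 0 | 1.000 | 0.050 | 90.0% / 90.0% | 91.6% / 91.6% |
| 0.25 | 1.008 | 0.048 | 90.2% / 90.4% | 91.3% / 91.6% |
| 0.5 | 1.030 | 0.043 | 90.7% / 91.6% | 90.6% / 91.6% |
| 0.75 | 1.067 | 0.037 | 91.4% / 93.3% | 89.4% / 91.6% |
| 1.0 | 1.116 | 0.029 | 92.4% / 95.1% | 87.5% / 91.6% |

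On the within-site reading, power without site equals 90% at D = 0.635, or 0.635 × 2.5 = 1.6 Finnegan points.

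Simulation agrees (20,000 trials, blocks of 4 and 6 assumed, within-site reading). At D = 0.5, alpha is 0.042 without site and 0.049 with it, and power 90.3% and 91.3%. At D = 1.0, alpha is 0.028 and 0.050, and power 87.0% and 91.4%.

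**3. Planned mixed model.** The stated 0.80 and 0.95 imply standard errors of 0.80/3.2415 = 0.247 and 0.95/3.2415 = 0.293. Dividing by √(2/115) gives infant-mean SDs of 1.87 and 2.22. For a constant gap of 1.25 points:

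- Within-site reading: k = 1.053 and 1.038; alpha 0.039 and 0.042; power 88.0% and 88.6%, against 90% with site.
- Total reading: alpha 0.038 and 0.041; power 91.3% against 93.0%, and 90.9% against 92.2%.

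**4. Aim 3.** By simulation with 120 children retained at random (60 per group), alpha without site is 0.046 at D = 0.5 and 0.040 at D = 1.0. This is closer to 0.05 than in Aim 1, because random loss weakens the within-site balance. On the within-site reading, power is 89.4% without site against 90.8% with it at D = 0.5, and 85.5% against 90.9% at D = 1.0. The logistic impairment model was not evaluated.

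**5. Gender.** If it is balanced by design and split about 50/50, k = √(1 + 0.25 G²) for a gender gap of G SD. G = 0.25 gives alpha 0.048 and G = 0.5 gives 0.043.

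**6. If site were offered to model selection.** Keeping site when p < 0.05, as a stand-in for the plan's fit rule, retains it in 47%, 96%, 100% and 100% of trials at D = 0.25, 0.5, 0.75 and 1.0. Power is then within 0.1 point of always including it.

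**The case against.** The strongest reply is that no harm is documented. There is no bias and no type I inflation, no between-site difference is given, and a gap of 0.25 SD costs about a quarter of a power point. This stands, and it limits how much weight the point can carry.

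Next, results below 90% need assumptions to stack up: SD 2.5 must be within-site, the gap must be large, and for the models site must never be offered. This also stands. If the within-site SD were 2.0, the lower end of the plan's range, power for 1.1 without site would be about 97% even at a 2.5-point gap: 1.1/(2.0 × √(2/115)) = 4.17, k = 1.176, Φ(4.17 − 1.96 × 1.176) = 0.969.

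Third, gender is already listed. It is, so only the lack of a commitment is at issue, and the gender figures presume that it is truly balanced by design.

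Fourth, the unadjusted tests are labelled initial, and the models carry the main questions. That is fair: the loss is certain to apply only to the initial tests, and reaches the models only if site is left out of them.

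Finally, Section 4.3.1 mentions additional variables in a sentence that ends without punctuation, so lost text cannot be excluded. As it reads, that sentence draws on medical-record and questionnaire histories, which do not clearly include site. Listed covariates that differ between sites, such as race, could absorb part of a site effect. None of this points to text that commits the analysis to site.

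**Conclusion.** The concern holds, as a modest point worth acting on because the remedy is nearly free. The analysis plan never names a factor that the randomisation stratifies on, and leaves the one balanced within it to discretion.

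If site is not prognostic, nothing is lost. For the Aim 1 single-time-point comparison, up to a gap of 0.5 SD the cost is at most about 1 power point. At 1.0 SD it is about 3 points (total-SD reading) or 4 points (within-site reading), with a true alpha near 0.029. For the planned mixed model, a 1.25-point gap costs about 1 to 2 points.

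These sizes rest on an assumed site gap, on site being absent from the model, and on no listed covariate standing in for it. The stated 90% is threatened only on the within-site reading of the SDs. The direction is certain: conservative, never anti-conservative.

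**What to change.** State in Section 4.3.1 that every between-group model pooling sites (Aims 1 and 3) includes site, as defined in the randomisation system, and gender as prespecified fixed effects, whatever the fit-based selection does with other factors. State also that the initial two-sample comparisons are site-adjusted or site-stratified, for example a van Elteren test in place of Mann-Whitney. Aim 2 is UMass only (Table 1) and needs no site term.

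The cost is a short addition to the analysis plan and a few degrees of freedom: one for gender, and one for site if it means UMass versus UPitt, or slightly more if it means hospital. Both factors are known at randomisation, so no further data are needed.
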